Our initial retrospective study suggests that QbMRI has adequate sensitivity to detect acute ciTBIs in children. The study was presented at 2 national conferences in the spring of 2016 (Society for Academic Emergency Medicine and Pediatric Academic Society) with a manuscript currently under review.¹² This preliminary study included all pediatric trauma patients presenting to OHSU from 2/2010 through 12/2013 who had both a head CT and QbMRI. The current standard of care in the pediatric ICU at OHSU is for patients admitted with an acute head injury to undergo routine QbMRI follow up to assess status of the injury rather than a repeat head CT. Our study team collected clinical data on these patients that included clinical interventions and then de-identified all head CT and QbMRI images for this cohort. The images were then independently reviewed by 2 neuroradiology fellows at OHSU (Please refer to **Figure 1**). The sensitivity of QbMRI to detect any radiographic injury was 85% (95% CI: 73, 93), but increased when evaluating clinically important TBIs to 100% (95% CI: 89, 100). The largest limitation of this study was the variable and often long time interval between acquisition of the head CT and QbMRI. The average length of time between the initial head CT and QbMRI was 27.5 hours with only 41% receiving both imaging tests within 12 hours of each other. Also, our preliminary data was collected by retrospective review. As such, it is very promising that our initial study had high sensitivity, but further prospective pilot data with a shorter interval between the index and reference test is needed to assess the discrepancy between the two types of lesions (radiographic vs clinically important) and feasibility of obtaining qbMRI in the setting of acute pediatric head trauma. While our study did not miss any clinically important TBIs, on further review of radiographic “missed lesions”, the study pediatric neurosurgeon noted signs of a healing bleed. This may suggest that they were “missed” because they were healed rather than present and not seen. All patients that did not have a lesion identified on QbMRI did not require significant clinical interventions and only underwent periods of observation in the hospital. However, this raises the need for a prospective trial to obtain QbMRI imaging within the same time frame sequentially after the initial head CT. The current proposed pilot study will provide further data to guide a larger, future multicenter study.

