QbMRIs will be obtained in the MRI scanner at OHSU available to the ED. The protocol will consist of a QbMRI protocol modified to include a blood-sensitive T2* sequence. No intravenous contrast will be administered. It is not anticipated that any sedation or anti-anxiety drugs will be administered to patients. However, this is reflected in the consent that a small portion of children will need for any type of neuroimaging. For this reason, parents may decline participation. No deep sedation drugs will be administered as that will fall under the definition of clinically unstable in the exclusion criteria. The protocol consists of:

- Coronal single-shot T2 weighted ultrafast spin echo
- Sagittal single-shot T2 weighted ultrafast spin echo
- Axial T2* weighted gradient recall echo

After a subject undergoes their imaging in the MRI suite, their further disposition will be selected by the attending physician as what they feel is necessary including admission to the hospital, observation or discharge.

Traumatic Brain Injury on neuroimaging will be defined as previously published¹ to include:

- Intracranial hemorrhage or contusion
- Cerebral edema
- Traumatic infarction
- Diffuse axonal injury
- Shearing injury
- Midline shift of intracranial contents or signs of brain herniation
- Skull fracture depressed by at least the width of the table of the skull
- Pneumocephalus

Number of Subjects:

A total of 100 subjects will be enrolled in this pilot study. To generate an approximate study timeframe and potential patient sample, EPIC was accessed to identify all patients less than 19 years of age who were seen in the OHSU emergency department in 2015 and had a “CT Head WO contrast (CPT code 70450)” performed while in the ED. This resulted 363 patients. As a large referral center, OHSU receives many transfers from outside hospitals. In our retrospective data of trauma system activations, the majority were transfer patients with head injuries. These numbers would not be included in the 363 most likely as their neuroimaging was done at an outside hospital. A review of the trauma registry at OHSU for the year of 2015 and patient less than 19 years of age resulted 221 patients who had head and neck injuries. There is most likely overlap between these 2 data points as some trauma registry patients were not transfers and underwent head CT in our department. However, we would conservatively expect that 400 patients may be eligible for this study during a 12 month period.

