
To assess the adequacy of this proposed pilot sample, we calculated the number of positive head CTs obtained in our department. Our rate of positive findings were better than the previous study mentioned rate of 2.5% positive head CTs of all ordered. At OHSU 10% of CTs in patients less than 19 years of age were positive for an acute intracranial injury. This was generated by applying the above search criteria in EPIC and associated an intracranial injury final diagnosis code including epidural hematoma, subdural hematoma, subarachnoid hemorrhage, intracranial bleed, skull fracture and cerebral contusion. This is a very conservative estimate as the majority of transfer patients through the trauma system will have positive neuroimaging as the reason for transfer and further pediatric subspecialty care. With these numbers we would expect to enroll the 100 patients within 1 year and have at least 10-20% with a positive acute TBI when taking into account the positive imaging rate in the OHSU emergency department and transfer patients with positive imaging.

Vulnerable Populations

This study, by design, is focused on pediatric patients. It may include other vulnerable populations such as pregnant women and minorities, though they are not the focus of the study

and are not included in screening criteria. No pregnant women will be given an MRI knowingly. Prisoners will not be included in this study.

Setting

The Doernbecher Children's Hospital emergency department

Consent Process

All parents will be consented on presentation to the emergency department by a member of the study team including the CRISP team. Please find attached consent form. All children ages 7-14 will be asked to signed the assent form as well.

We are requesting a consent/HIPAA waiver for a select group of patients. Any patient who is excluded from the study after initial screening for any reason other than the LAR refusing to be included will be reviewed by the principal investigator. If the clinical team, without any input from the research team, has obtained the same imaging test this study is evaluating, QuickBrain MRI, the study team will use the imaging and data as in the rest of the protocol under a waiver. It is not possible to obtain consent due to the short time window of being in the ED. Due to the acute nature of the injuries they do not have follow up in the ED either to allow consent.

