For patients who are excluded after the parent/LAR refuses the study, all charts will be reviewed. If the patient underwent the same imaging test this study is evaluating, QuickBrain MRI, by the clinical without any input from the research team, the patient family will be contacted by the study Principal Investigator as participation is generally declined in the trauma bay due to family stress. Unless at time of consent, study team noted reason for declining participation would be such that they would not be amenable to re-contact. The principal investigator will only discuss the study once with parents/LAR via phone number in EHR and detail that their child underwent the same imaging test we are studying. At that time, the principal investigator will ask for consent to include the patient in the study as nothing is needed in addition or further follow up. A telephone script has been uploaded to further detail this consent process.

Data Analysis:

All data will be entered into a RedCap database maintained on the OHSU network server requiring a username and password. Clinical data will consist of descriptive statistics. The primary outcome of whether a lesion was seen on QbMRI will be presented as sensitivity, specificity, negative predictive value and positive predictive value with 95% confidence intervals. The secondary outcome of whether patients need anxiolysis will be compared between head CT and QbMRI with an independent t-test. The QbMRI protocol will be described with language to describe the imaging.

Clearance of perivascular waist in the brain is critical for recovery after traumatic brain injury. Some of these clearance happens through a network of perivascular spaces surrounding the brain

vessels called the glymphatic system. When the glymphatic system becomes dysfunctional, enlarged perivascular spaces (ePVS) can be seen on MRI. The third outcome of this study is to evaluate the presence of ePVS in patients with concussion receiving an MRI during their emergency department evaluation. We hypothesize that changes in perivascular spaces happen over time, and therefore ePVS should not be present in these early studies.

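### Re-contacted refusers and waiver children enter only if clinicians had obtained a QbMRI, and the plan pools them undistinguished with the prospective cohort

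*Combined protocol and SAP*

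**What the plan says.** The Consent Process section has two late routes into the study.

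- **Refusers.** All their charts are reviewed. The condition for a call is "If the patient underwent the same imaging test this study is evaluating, QuickBrain MRI, by the clinical without any input from the research team". If it is met, "the patient family will be contacted by the study Principal Investigator", unless the "study team noted reason for declining participation would be such that they would not be amenable to re-contact". In that single call "the principal investigator will ask for consent to include the patient in the study".
- **Children excluded for any reason other than refusal.** If the clinical team had independently obtained a QbMRI, "the study team will use the imaging and data as in the rest of the protocol under a waiver".

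The main route is different. Under Study Design and Study Procedure, consent comes first, the physician then orders a study QbMRI to follow the head CT, and the scan is done during the emergency department visit.

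Data Analysis plans sensitivity, specificity, PPV and NPV with 95% confidence intervals; Outcomes adds likelihood ratios. Neither section mentions entry route, a separate analysis set or a sensitivity analysis. Number of Subjects does not say whether late entrants count toward the 100.

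**The concern.** A refuser without a clinical QbMRI is never called, and an excluded child without one is never used. Who enters late therefore depends on who gets a clinical QbMRI. The protocol describes one such use in head injury. Preliminary Data says that standard care in the pediatric ICU is for "patients admitted with an acute head injury to undergo routine QbMRI follow up to assess status of the injury", in place of a repeat CT. A child sent home after a negative CT has no described path to that scan, whereas a child admitted to the ICU does.

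Two things are at stake. First, late entrants are likely to include more CT-positive children than the consented cohort, which changes the prevalence behind PPV and NPV. Second, they may be scanned much later. Preliminary Data names the long CT-to-QbMRI interval as the main limitation of the retrospective study, suggests that some missed lesions had healed, and gives this as the reason for a prospective study. Nothing in the plan keeps late scans out: the only time limit, in the Exclusion criteria, is 6 hours and covers outside-hospital CTs alone. The waiver route can also admit children who failed an eligibility criterion.

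**Working it through.** **1. The plan's own figure.** Number of Subjects expects at least 10-20% of the 100 to be positive and gives no derivation. Its inputs are 363 emergency department head CTs, 10% of them positive, and 400 eligible children a year. Reading 400 − 363 = 37 as added transfers, and assuming 50% to 100% of those are positive:

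- (36.3 + 18.5)/400 = 13.7%
- (36.3 + 37)/400 = 18.3%

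Both lie inside the stated range, so 15% is a fair base prevalence for the consented cohort.

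**2. The interval.** In the retrospective series the average CT-to-QbMRI interval was 27.5 hours, and 41% had both tests within 12 hours (Preliminary Data). The main route places the QbMRI in the same emergency visit as the CT.

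**3. Effect on PPV and NPV.** Assumed, because the documents do not give them: sensitivity (Se) 90%, specificity (Sp) 95%, the number k of late entrants among 100, and the CT-positive share q among them.

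- Prevalence p = [0.15 × (100 − k) + q × k]/100
- PPV = Se·p / [Se·p + (1 − Sp)(1 − p)]
- NPV = Sp(1 − p) / [Sp(1 − p) + (1 − Se)p]

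| k | q | p | PPV | NPV | Share of CT-positives from late routes |
|---|---|---|---|---|---|
| 0 | – | 15% | 0.135/0.1775 = 76.1% | 0.8075/0.8225 = 98.2% | 0 |
| 5 | 50% | (14.25 + 2.5)/100 = 16.75% | 0.15075/0.192375 = 78.4% | 0.790875/0.807625 = 97.9% | 2.5/16.75 = 15% |
| 10 | 80% | (13.5 + 8)/100 = 21.5% | 0.1935/0.23275 = 83.1% | 0.74575/0.76725 = 97.2% | 8/21.5 = 37% |
| 20 | 80% | (12 + 16)/100 = 28% | 0.252/0.288 = 87.5% | 0.684/0.712 = 96.1% | 16/28 = 57% |

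Se and Sp are held fixed here. That is correct if entry depends on the CT result alone, because both are computed within CT-positive or CT-negative children. The likelihood ratios are then unchanged too.

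**4. When sensitivity moves.** It moves only if the added CT-positive children differ from the other CT-positive children. Take the retrospective sensitivity for any radiographic injury (85%), a base prevalence of 10% and 10 late entrants. The consented 90 then supply 9 positives.

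- Late entrants have more severe injury, sensitivity assumed 100%: (0.85 × 9 + 5)/14 = 90.4% if 5 are positive; (0.85 × 9 + 10)/19 = 92.9% if all 10 are.
- Late entrants have healing lesions, sensitivity assumed 70%: (0.85 × 9 + 3.5)/14 = 79.6%; (0.85 × 9 + 7)/19 = 77.1%.

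The two mechanisms pull in opposite directions, and the documents do not show which would prevail.

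**The case against.** Several stronger readings are tempting, and the case against them is good.

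- **A reader might infer that entry depends on the CT result.** No section says so. The trigger is a clinical QbMRI; the follow-up practice is stated for the pediatric ICU only, and Study Procedure says QbMRI is available to the emergency department at all hours for other indications. A CT-negative refuser with such a scan would also be called. The link to CT result is a reasonable inference, not a rule.
- **A reader might infer that all the accuracy estimates are biased.** Selection on CT result alone leaves sensitivity, specificity and both likelihood ratios intact. These are four of the six primary measures, and the hypothesis concerns the first two.
- **A reader might infer that clinical scans lack T2\*.** Study Procedure does call the study version "a QbMRI protocol modified to include a blood-sensitive T2* sequence", while the late routes accept a clinical scan as the same test. But the Figure 1 caption shows a T2\* image acquired within a QbMRI. A difference is possible, not shown.
- **A reader might infer that prevalence is raised artificially.** The Consent Process section says refusal generally happens in the trauma bay under family stress. If those children are more severely injured, omitting them also distorts the case mix, and re-contact may partly restore it.

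The route may also be thin: it needs a refusal, a clinical QbMRI, no noted bar to re-contact, one call and then consent. And an in-house CT carries no time limit for any child, so delay is not confined to late entrants.

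These points limit the size and certainty of the effect. They do not supply what is missing: a reader of the results could not separate the prospective cohort from children scanned as in the retrospective series.

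**Conclusion.** The concern holds in a limited form. Both late routes admit children on the basis of a clinician-ordered QbMRI, and the plan does not distinguish them afterward. Given the site's described practice, these children are probably more often CT-positive and scanned later.

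On the assumptions of step 3, pooling raises PPV by about 2 to 11 percentage points and lowers NPV by about 0.3 to 2. The number of late entrants and their CT-positive share are not in the documents, so this is a range of scenarios, not an estimate. An effect on sensitivity is possible but has no known direction. With only 10-20 positives expected, a few such children could matter.

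This should be corrected because the pilot is meant to guide a multicenter study, but it does not undermine the design.

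**What to change.** 1. Record for every child the entry route (prospective consent, re-contact or waiver), the CT-to-QbMRI interval and the sequences acquired.
2. Define the primary accuracy set as children consented before a study QbMRI, and count the 100 on that set.
3. Report the 2x2 table for re-contacted and waiver children separately, with their intervals, and add a pooled analysis of all children as a sensitivity analysis.

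No data are discarded. The work is three variables, one definition and one or two extra tables. Accrual of the 100 would be somewhat slower. The primary set would also hold fewer CT-positive children than a pooled 100 (about 15 against 16.75 to 28 in the scenarios above), so its sensitivity interval would be wider. That loss is relative to the pooled set only: 100 prospective enrollments keep the planned 10-20% positive.

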Magnetic Resonance Imaging (MRI) does not use ionizing radiation and has been shown to be accurate for detecting traumatic brain injury.^{4,5} However, MR imaging takes longer to obtain than CT and requires patients to hold still for an extended period of time, often requiring sedation and limiting its use in acute injuries among pediatric patients. An abbreviated “Quick” brain MRI (QbMRI) protocol includes single-shot T2 weighted ultrafast spin echo images acquired in the axial, sagittal, and coronal planes. Images can be obtained in approximately 1-3 minutes. QbMRI has been previously studied for evaluating ventriculoperitoneal shunt failure in children with hydrocephalus and was found to be equally accurate to CT with approximately 4% of patients needing anxiolysis/sedation in both CT and MRI groups.⁶ In a recent survey of institutions with a pediatric neurosurgeon on staff, approximately 80% have QbMRI capabilities, but its clinical utility remains uncertain as over 97% of these institutions still use CT for pediatric head trauma.⁷⁻⁹ However, the effectiveness of QbMRI to diagnose ciTBI in the acute setting is unknown and has not been studied in a prospective manner. This subject is very important to improve the care we provide as pediatrics makes up the majority of acute head injuries seen in

emergency departments in combination with the increased radiosensitivity of their tissue and risk for malignancy.^{10,11}

Preliminary Data:

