Specific Aims:

There are 3 specific aims for this study during the grant period:

- D. Develop a feasible protocol for obtaining QbMRI for children presenting to the emergency department with acute head injury.
- E. Prospectively test the diagnostic accuracy of qbMRI for detection of acute pediatric TBI in the emergency care setting compared to head CT as the reference standard.
- F. Evaluate the feasibility of obtaining QbMRI in the emergency department to assess acute pediatric brain injury, including need for sedative medications, time to imaging, and provider satisfaction.

Outcomes:

1. Primary Outcome: Test characteristics of QbMRI to detect acute pediatric TBIs, including sensitivity, specificity, positive/negative predictive value and positive/negative likelihood ratios.
2. Secondary Outcomes: Develop formal protocol to be employed for further clinical evaluation and trials on QbMRI in pediatric head trauma; assess feasibility of obtaining QbMRI in the emergency department to include need for anxiolysis/sedation, time to imaging and provider satisfaction.

Hypothesis:

We hypothesize there is no significant difference of sensitivity and specificity of QbMRI for detection of clinically important traumatic brain injuries as compared to non-contrast head CT in patients less than 15 years presenting with head trauma. We hypothesize that it will be feasible to obtain QbMRI in the emergency department without increased use of anxiolysis/sedation or prolonged time to obtain imaging

4. Study Design:

Overview: The study will be a prospective cohort study of diagnostic accuracy comparing QbMRI (index test) to non-contrast head CT (reference test). Children being evaluated for acute TBI with head CT will then undergo QbMRI in the emergency department. Only subjects who the attending physician has decided to obtain neuroimaging in will be enrolled; therefore subjects will not undergo imaging just for the study. The results of the QbMRI will not be used for clinical care. All images will be de-identified prior to review by the neuroradiologist including patient name, hospital and date.

5. Study Population:

Inclusion criteria:

1. The patient presents to the pediatric emergency department or trauma system at OHSU or is a trauma system transfer patient to OHSU
2. Age 0-14 years.
3. Being evaluated for a traumatic head injury and attending physician decides to obtain a head CT.

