4. Clinically stable for additional testing: provider deems it safe to obtain a QbMRI in the ED without deep sedation

Exclusion criteria:

1. Subject is from outside hospital and head CT was performed greater than 6 hours prior
2. Subject is from outside hospital and initial head CT is not in our imaging system for review
3. History of intracranial surgery
4. History of metallic implants making MRI contraindicated
5. Decompressive surgery prior to QbMRI

Study Procedure:

The Clinical Research Investigative Study Program (CRISP) volunteers who are on duty in the emergency department between the hours of 7 am and 11 pm will screen all ED patients for eligibility including pediatric trauma system entries. They will identify possible subjects based on suggestive chief complaints (e.g. head injury, trauma, fall, etc.) and approach the attending physician about whether the subject is being evaluated for possible acute head injury and will be receiving neuroimaging. If so, they will approach the family and review the consent forms with them for participation. After subjects are found to be eligible (see above inclusion/exclusion criteria) and consented, the physician will order the study QbMRI to be done after the head CT. QbMRIs are available to our pediatric ED at all hours as it is standard of care for other indications as described previously. Subjects will only be enrolled in the study if the attending physician feels they warrant neuroimaging with a head CT. After undergoing a QbMRI, their clinical care will be the same whether they are in the study or not. A copy of the images will then be de-identified and placed in separate review folders in the electronic radiology system so they cannot be linked (ie. One folder for head CTs and one folder for QbMRIs) for review by an attending neuroradiologist. Clinical data including length of stay, procedures performed and disposition will be collected directly from EPIC.

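### Need for anxiolysis is a yes/no outcome compared between two scans of the same child, but the plan assigns it an independent t-test, which ignores the pairing and cannot by itself support a claim of no increase

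*Combined protocol and SAP*

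**What the plan says.** Data Analysis gives one sentence to this outcome: "The secondary outcome of whether patients need anxiolysis will be compared between head CT and QbMRI with an independent t-test". It is the only test named for the feasibility hypothesis. The 95% confidence intervals in that section are attached to the accuracy measures only.

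The design is within-child. Study Design (Overview) says "Children being evaluated for acute TBI with head CT will then undergo QbMRI in the emergency department", and Study Procedure says "the physician will order the study QbMRI to be done after the head CT".

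The Hypothesis section expects QbMRI to be feasible "without increased use of anxiolysis/sedation or prolonged time to obtain imaging". No margin, significance level or interval is given for that statement.

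On the expected frequency, Background cites an earlier shunt study with "approximately 4% of patients needing anxiolysis/sedation in both CT and MRI groups", and Study Procedure adds "It is not anticipated that any sedation or anti-anxiety drugs will be administered to patients".

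On data capture, Study Procedure says "Clinical data including length of stay, procedures performed and disposition will be collected directly from EPIC". Anxiolysis at each scan is not among the items named.

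**The concern.** There are two separate faults.

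**The pairing is ignored.** Each child with both scans contributes a yes/no result to each side. The independent t-test treats these as two unrelated groups, so its p-value depends only on the two totals. The information about a within-child difference lies in the discordant children, that is, those medicated for one scan and not the other. The t-test never uses that split.

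**The test does not match the claim.** The hypothesis is that use does not increase. A non-significant difference test does not show this, least of all with few events. Without a margin or an interval, nothing in the plan separates no increase from too little information to tell.

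The direction of the first fault is not fixed. If need for medication is strongly positively correlated within a child, the t-test is too conservative and can miss a real increase, which favours the hypothesis. If the correlation is near zero, or no child is medicated for CT, it can be less lenient to the hypothesis than an exact paired test.

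Need for sedative medication appears in the objectives, aims, outcomes and hypothesis, and the pilot is meant to guide a larger multicenter study. A misread feasibility result would carry forward.

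**Working it through.** The plan gives no power, margin or expected difference for this comparison, so there is no figure of its own to reproduce.

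**Inputs**
- n = 100 children (Number of Subjects).
- CT rate 4% (the shunt-study rate in Background).
- QbMRI rate 10%: assumed, for illustration.
- Number medicated for both scans: not given, so every possible value from 0 to 4 is shown.
- Two-sided 0.05: assumed.

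Let b be the children medicated for QbMRI only and c those medicated for CT only.

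**Independent t-test.** t = 0.06 / √[(0.04×0.96 + 0.10×0.90)/99] = 0.06/0.0360 = 1.67 on 198 df, p = 0.097. The overlap does not enter.

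**Standard errors of the difference**
- Independent: √[(0.04×0.96 + 0.10×0.90)/100] = 0.0358.
- Paired: √{[(b+c)/n − ((b−c)/n)²]/n}.
- Full overlap (b = 6, c = 0): √[(0.06 − 0.0036)/100] = 0.0237, so the independent value is 51% too large.
- No overlap (b = 10, c = 4): √[(0.14 − 0.0036)/100] = 0.0369, so it is 3% too small.

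**McNemar.** Exact p = 2·P[Bin(b+c, ½) ≤ min(b,c)]. The mid-p version subtracts P[Bin(b+c, ½) = min(b,c)]. At full overlap, exact p = 2×(½)⁶ = 0.031.

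| Medicated for both | b, c | t-test p | Exact McNemar p | Mid-p | Independent vs paired SE |
|---|---|---|---|---|---|
| 4 | 6, 0 | 0.097 | 0.031 | 0.016 | +51% |
| 3 | 7, 1 | 0.097 | 0.070 | 0.039 | +30% |
| 2 | 8, 2 | 0.097 | 0.109 | 0.065 | +15% |
| 1 | 9, 3 | 0.097 | 0.146 | 0.092 | +5% |
| 0 | 10, 4 | 0.097 | 0.180 | 0.118 | −3% |

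The paired 95% score (Tango) interval for the 6-point difference is 2.1 to 12.5 points at full overlap and −1.5 to 14.2 points at none.

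**Counter-case.** With QbMRI 5 and CT 0 of 100, the t-test gives p = 0.024, exact McNemar 0.0625 and mid-p 0.031. Here the t-test is the less lenient of the three to the no-increase hypothesis.

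**Power to detect 4% vs 10%** (n = 100, exact multinomial enumeration):

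| Within-child correlation | t-test | Mid-p McNemar | Exact McNemar |
|---|---|---|---|
| 0 | 39% | 37% | 28% |
| 0.3 | 36% | 48% | 37% |
| 0.6 | 31% | 71% | 55% |

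The largest possible correlation for these rates is (0.04 − 0.004)/√(0.04×0.96×0.10×0.90) = 0.61, so the last row is close to a limiting case. In every row the t-test misses a 2.5-fold increase more than 60% of the time.

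**What equal rates would show.** With 4 vs 4 of 100, the paired upper 95% limit is 3.7 points (all four the same children) to 6.5 points (no overlap). If only 50 children had both records (assumed; 2 vs 2), it is 7.1 to 10.2 points.

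**The case against.** The strongest reply is about weight. This is a secondary feasibility outcome in a 100-child pilot, and the primary accuracy result does not depend on it. Few events are expected, so no test will say much, and the 10% QbMRI rate has no source in the documents. On 0/1 data with 100 per group, a t-test is close to a two-proportion test. McNemar is not uniformly better: the exact version has less power than the t-test at zero correlation (28% vs 39%) and about the same at 0.3. All of this is true. It limits the severity and shows that changing the test alone gains little. It does not make an unpaired analysis right for paired data, and scarce events strengthen the case for an interval.

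Three further points stand as qualifications:
- Not every analysed child need have a CT–QbMRI pair. The waiver route in Consent Process admits some children who were excluded at screening but had a clinical QbMRI. Transfers may have had their CT elsewhere, since the exclusion applies only when "Subject is from outside hospital and head CT was performed greater than 6 hours prior". That each scan's status will be recorded is inferred from the planned comparison.
- CT comes first, so a drug given for CT may still be acting at QbMRI. No paired statistic settles which scan it belongs to.
- Parents may decline because of possible sedation, and inclusion requires that QbMRI be judged safe without deep sedation. This selection limits any general no-increase claim, whichever test is used.

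**Conclusion.** The concern holds. The named test does not fit a binary, within-child comparison, and no other section supplies a paired method, an interval or a margin. In the worked example the t-test p-value stays at 0.097 while the exact paired p-value moves across 0.05 (0.031 to 0.180), with the standard error wrong by +51% to −3%. The direction depends on a correlation that the documents do not give, so this is not a one-way bias. Separately, non-significance cannot carry the no-increase hypothesis under any of these tests: equal observed rates in 100 pairs still allow an increase of 3.7 to 6.5 points.

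These sizes rest on the 4% rate from a different population and on assumed values for the QbMRI rate, the overlap and the number of complete pairs. The mismatch between test and design rests on none of them. It should be fixed, but it does not threaten the primary outcome.

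**What to change.** In Data Analysis, replace the t-test sentence with the following:
- Report the paired 2×2 table and the difference in proportions (QbMRI minus CT) with a 95% score interval, supported by a McNemar test, mid-p or exact, chosen in advance.
- Analyse children with anxiolysis status recorded for both scans. Report that number, and describe who is missing, because transfers and waiver-route children may be missing selectively.
- Judge any statement of no increased use by the upper confidence limit against a margin that the investigators set in advance. If they set none, call the comparison descriptive.

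In Study Procedure, name anxiolysis status for each scan as a data item, and define beforehand how a drug given before both scans is recorded.

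The cost is a short text edit, one margin (or the word descriptive) and one data item per scan, with no extra patients or procedures. The drawback is that complete pairs may number fewer than 100. At an assumed 50 pairs, the upper limit for equal observed rates widens to 7.1 to 10.2 points.
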